### 12.2 Tables

No.	Title of table	Analysis Population/Dataset
14.1 – Study		
	Subjects Disposition	All Subjects

No.	Title of table	Analysis Population/Dataset
	Analysis Population	All Subjects
	Demographics and Baseline Characteristics	Safety, PK
	Summary of Prior and Concomitant Medications	Safety
14.2 – Pharmacokinetics		
	Descriptive Statistics for Plasma Concentrations	PK
	Descriptive Statistics for Plasma Pharmacokinetic Parameters - Non-Compartmental Analysis	PK
	Descriptive Statistics for Plasma Pharmacokinetic Parameters - Compartmental Analysis	PK
14.3 – Safety		
	Summary of Treatment Emergent Adverse Events	Safety
	Treatment Emergent Adverse Events by System Organ Class and Preferred Term	Safety
	Treatment Emergent Adverse Events by System Organ Class, Preferred Term and Severity	Safety
	Treatment Emergent Adverse Events by System Organ Class, Preferred Term and Relation to Study Drug	Safety
	Summary of Routine safety laboratory tests - Hematology	Safety
	Summary of Routine safety laboratory tests - Biochemistry	Safety
	Summary of Routine safety laboratory tests - Coagulation	Safety
	Summary of Routine safety laboratory tests - Urinalysis	Safety
	Summary of Routine safety laboratory tests - Overall Evaluation	Safety
	Shift table of Routine safety laboratory tests - Urinalysis	Safety
	Body weight	Safety
	Vital Signs	Safety
	Vital Signs - Overall Evaluation	Safety
	Routine Safety 12-Lead ECG	Safety
	Routine Safety 12-Lead ECG - Overall Evaluation	Safety
	Routine Safety 12-Lead ECG - Number of Subject Meeting QTcF Criteria	Safety

## 12.3 Figures

No.	Title of figure	Analysis Population/Dataset
14.2 – Pharmacokinetics		
	Profile of Mean Plasma Concentrations – PK	PK
	Profile of Mean observed and predicted Plasma Concentrations - Compartmental Analysis - PK	PK
16.2.6 – Pharmacokinetics		
	Profile of Individual observed and predicted Plasma Concentrations by Subjects - Compartmental Analysis	PK

No.	Title of figure	Analysis Population/Dataset
	Profile of Individual observed Plasma Concentrations by Each Group	PK

### 13. REVISION HISTORY FOR SAP AMENDMENTS

Version 2.0 (25 January, 2019)

It reflected the results of the data review meeting on 17 January, 2019.

In List of PK Parameters, the PK parameters were matched with those described in PK Parameter Calculations in Appendix 1 and 2.

In Section 1, description of Section 3 has been deleted because Holter ECG analysis was not described.

At the beginning of Section 2, “In this SAP, the analyses with underline are not planed.” was added, and the contents of analysis in Section 2.1.1, 2.1.3 and 2.1.4 were underlined.

## APPENDIX 1 – CALCULATION OF PHARMACOKINETIC PARAMETER USING NON-COMPARTMENTAL ANALYSIS

- Actual blood sampling times for the assay of MCI-186 will be used in the calculation of pharmacokinetic parameters
- All concentrations below the LLOQ will be set at zero for pharmacokinetic calculations
- Calculation of pharmacokinetic parameters will be used 1/Y weighting of the data
- When  $\lambda_z$  is missing (or cannot be determined),  $AUC_{0-\infty}$ ,  $AUC\%_{ex}$ , MRT, CL,  $V_{ss}$ ,  $V_z$ , Lower limited of  $\lambda_z$ , Upper limited of  $\lambda_z$  and Number of  $\lambda_z$  points will not be calculated

[figure not shown]
PK Parameter Calculations		
Parameters	Unit	Calculation
$AUC_{0-\text{last}}$	h·ng/mL	will be calculated using the linear trapezoidal method and actual times $AUC_{0-\text{last}} = \sum_{i=1}^n \frac{t_i - t_{i-1}}{2} (C_{i-1} + C_i)$
$AUC_{0-24h}$	h·ng/mL	will be calculated using the linear trapezoidal method and zero to 24h of actual times
$AUC_{0-\infty}$	h·ng/mL	$AUC_{0-\infty} = AUC_{0-\text{last}} + \frac{C_{\text{last}}}{\lambda_z}$
$AUC\%_{ex}$	%	$AUC\%_{ex} = \frac{AUC_{0-\infty} - AUC_{0-\text{last}}}{AUC_{0-\infty}} \times 100$
$C_{\text{max}}$	ng/mL	will be determined using maximum drug concentration
CL	L/h	$CL = \frac{\text{Dose}}{AUC_{0-\infty}}$

PK Parameter Calculations		
Parameters	Unit	Calculation
$\lambda_z$	1/h	
The exponential rate constant of the terminal phase, <math>\lambda_z</math>, will be estimated by log-linear regression, if determinable. The number of data points included in the regression will be determined by visual inspection. Wherever possible, a minimum of 3 data points will be used in the estimation of <math>\lambda_z</math>.
 
During the analysis, this calculation method repeats regressions using the last three points with non-zero concentrations, then the last four points, last five, etc. Points prior to <math>C_{max}</math> or prior to the end of infusion will not be used unless the user specifically requests that time range. Points with a value of zero for the dependent variable will be excluded. For each regression, an adjusted <math>R^2</math> will be computed
 $\text{Adjusted } R^2 = 1 - \frac{(1 - R^2) + (n - 1)}{(n - 2)}$ 
where <math>n</math> is the number of data points in the regression and <math>R^2</math> is the square of the correlation coefficient.
 
The regression with the largest adjusted <math>R^2</math> will be selected to estimate <math>\lambda_z</math>, with these caveats:
 
If the adjusted <math>R^2</math> does not improve, but is within 0.0001 of the largest adjusted <math>R^2</math> value, the regression with the larger number of points will be used. <math>\lambda_z</math> must be positive, and calculated from at least three data points.

Lower limited of $\lambda_z$	h	will be determined using lower limit on time to be included in the calculation of $\lambda_z$
MRT	h	$\text{AUMC}_{0-\infty} = \sum_{i=1}^n \frac{(t_i - t_{i-1})(t_i \times C_i + t_{i-1} \times C_{i-1})}{2} + \frac{t \times C_t}{\lambda_z} + \frac{C_t}{(\lambda_z)^2}$ $\text{MRT} = \frac{\text{AUMC}_{0-\infty}}{\text{AUC}_{0-\infty}} - \frac{\text{TI}}{2}$ 
where TI represents infusion duration.

Number of $\lambda_z$ points	-	will be determined using number of points used in computing $\lambda_z$ . If $\lambda_z$ cannot be estimated, zero.
$t_{1/2}$	h	$t_{1/2}$ will be determined as: $t_{1/2} = \frac{\log_e(2)}{\lambda_z}$

PK Parameter Calculations		
Parameters	Unit	Calculation
$t_{max}$	h	will be determined using time to maximum drug concentration
Upper limited of $\lambda_z$	h	will be determined using upper limit on time to be included in the calculation of $\lambda_z$
$V_{ss}$	L	$V_{ss} = MRT \times CL$
$V_z$	L	$V_z = CL \times \frac{1}{\lambda_z}$

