## **6.5 Pharmacokinetic assessments**

Blood samples for MCI-186 will be collected pre-dose and no sooner than 5 minutes but no later than 7 minutes after the timepoints in relation to start of infusion at 30, 60, 75, 90, and 105 min; and no sooner than 5 minutes but no later than 10 minutes after the timepoints in relation to start of infusion at 2, 3, 4, 6, 8, 12 and 24 hours.

The analysis will be performed only on samples from subjects receiving active drug.

Blood samples will be packed in dry ice and sent by courier to:

[REDACTED]

Primary samples will be sent by courier from study center to [REDACTED]

[REDACTED] Contingency samples will be shipped after primary samples arrive.

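### The adjusted R-squared printed in SAP Appendix 1 adds (n − 1) where it should multiply; applied literally, the terminal-slope rule would count points rather than judge fit

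*SAP*

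**What the plan says.** The λz row of SAP Appendix 1 sets out a log-linear regression and two ways of choosing its points.

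- **By eye:** "The number of data points included in the regression will be determined by visual inspection".
- **By search:** "this calculation method repeats regressions using the last three points with non-zero concentrations, then the last four points, last five, etc". Points before Cmax "or prior to the end of infusion will not be used unless the user specifically requests that time range". The row continues: "Points with a value of zero for the dependent variable will be excluded. For each regression, an adjusted" R-squared is calculated, printed as 1 − [(1 − R²) + (n − 1)]/(n − 2), where n is the number of points and R² the squared correlation. "The regression with the largest adjusted" R-squared is then used. If a candidate is within 0.0001 of the largest value, "the regression with the larger number of points will be used".

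The row does not say which of the two prevails. Appendix 1 also specifies 1/Y weighting and sets values below the LLOQ to zero, which removes them from this regression. Appendix 2 describes the decline with a three-compartment model. SAP section 11 names Phoenix WinNonlin for the PK parameters.

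**The concern.** An adjusted R-squared should approach 1 for a good fit and penalise extra points that do not help. The printed expression has a plus sign between (1 − R²) and (n − 1) where a product belongs, and it does neither. A rule that maximises it would favour the longest regression available. With a multiphasic decline, the longest regression includes the steep early phases, so λz is too large and the terminal half-life too short.

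PK parameters are a secondary endpoint in both documents, and Appendix 1 is where their calculation is specified. Anyone reproducing λz from the SAP text would select the wrong points.

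**Working it through.** The plan states no half-life or number of λz points under this rule, so there is no figure of its own to reproduce.

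**1. Algebra.** 1 − [(1 − R²) + (n − 1)]/(n − 2) = [(n − 2) − (1 − R²) − (n − 1)]/(n − 2) = (R² − 2)/(n − 2). Since R² lies between 0 and 1, the value lies between −2/(n − 2) and −1/(n − 2). It is always negative, and a perfect fit scores −1.000 at n = 3, −0.500 at n = 4 and −0.111 at n = 11.

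| n | R² | As printed | Multiplied: 1 − (1 − R²)(n − 1)/(n − 2) |
|---|---|---|---|
| 3 | 0.99 | −1.01 | 0.98 |
| 3 | 0.9999 | −1.0001 | 0.9998 |
| 11 | 0.93 | −0.1189 | 0.9222 |

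The printed form prefers 11 points at R² = 0.93 to 3 points at 0.9999. The multiplied form prefers the 3.

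**2. How rarely an extra point is refused.**
- 4 against 3: the worst 4-point score is −2/2 = −1 and the best 3-point score is −1/1 = −1, so 4 points never lose.
- 5 against 4 with R² = 0.99: the 4-point score is −1.01/2 = −0.505. Five points lose only if (2 − R²)/3 > 0.505, that is, R² < 0.485.
- 11 against a perfect 10: 11 points win if (2 − R²)/9 < 1/8, that is, R² > 0.875.
- The tie rule does not help: perfect-fit scores at n = 10 and n = 11 differ by 1/8 − 1/9 = 0.0139, far more than 0.0001.

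**3. Points available.** Protocol section 6.5 samples at "timepoints in relation to start of infusion at 30, 60, 75, 90, and 105 min", then at 2, 3, 4, 6, 8, 12 and 24 h. From the 60-minute sample on, that is 4 + 7 = 11 points, fewer if late samples fall below the LLOQ.

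**4. Size.** Three-phase profiles were simulated at the protocol sampling times. AUC was scaled to the 1364.7 ng·hr/mL of protocol section 3.4.1 for 60 mg, and to about five times that for 300 mg. Phase half-lives, noise and LLOQ are assumptions. The printed rule took every available point in about 100% of profiles (median 9 to 11); the multiplied rule took a median of 3 to 5. Median t½ with 1/Y weights:

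| Assumed terminal t½; dose; LLOQ (ng/mL); noise | Printed (h) | Multiplied (h) | Shorter by |
|---|---|---|---|
| 3 h; 300 mg; 1; 20% | 2.65 | 2.76 | 1 − 2.65/2.76 = 4% |
| 4 / 5 / 6 h; 300 mg; 0.5; 8% | 3.5 / 4.1 / 4.5 | 3.9 / 4.7 / 5.4 | 10 / 13 / 17% |
| 4 / 5 / 6 h; 60 mg; 0.5; 8% | 2.2 / 2.2 / 4.5 | 2.9 / 2.9 / 5.4 | 24 / 24 / 17% |
| 9 h; 300 mg; 1; 10% | 5.46 | 7.06 | 23% |

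A repeat of the 60 mg setting gave 17 to 26%. In a few settings with an LLOQ of 5 ng/mL the ratio of medians was somewhat larger (1.86 against 2.68 h, 31%).

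**5. Which parameters move.** Vz = CL/λz moves almost in proportion to t½. AUC0-∞ = AUC0-last + Clast/λz, and the extrapolated part was at most about 1.2% of the total in the runs that examined it. Cutting that part by 26% changes AUC0-∞ by about 1.2% × 0.26 = 0.3%. Runs with 1/Y weights gave 0.02 to 0.4% for AUC0-∞, with CL moving correspondingly, and 0.4 to 5.5% for MRT. Vss = MRT × CL follows MRT.

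**The case against.** The strongest objection is that the formula may never be used. WinNonlin calculates the parameters, the row reads like a description of its search, and no passage says that the expression will be coded by hand. Hand-coding would also expose the slip at once, because a perfect 3-point fit scores −1. This stands: the documents show a wrong specification, not a biased result.

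Second, the visual-inspection sentence lets an analyst reject a line drawn through a visibly curved profile. That stands as mitigation, but because the row gives no order of precedence, it cannot be relied on as a safeguard.

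Third, the sizes rest on inputs the documents do not give, and the multiplied form is itself imperfect. At 60 mg it returned 2.9 h for assumed terminal half-lives of 4 and 5 h, a miss of about 28% and 42%. This limits how far any percentage can be pressed. It does not affect the algebra or the direction.

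Fourth, the plus sign might be a misread multiplication sign. That is unlikely, since multiplication signs elsewhere in the same table (AUC%ex, MRT, Vss, Vz) were read correctly, but the original page should be checked.

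A reader might also infer a half-life roughly halved. Unweighted fits at 300 mg do give 43 to 57% shortening, but the SAP specifies 1/Y weighting, so that is not the size for this plan.

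**Conclusion.** The printed adjusted R-squared is wrong, and the selection rule built on it does not measure fit. If it were applied literally, nearly every quantifiable point from Cmax or the end of infusion would enter the terminal regression. Under the multiphasic decline assumed in Appendix 2, t½ would be too short, by roughly 4 to 26% with 1/Y weights given the assumed half-lives, noise and LLOQ.

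The material effects are on λz, t½ and Vz, with smaller ones on MRT and Vss. A reader might infer from the formulas that AUC0-∞ and CL are seriously affected too. They are not, because sampling to 24 h leaves little area to extrapolate. Cmax, AUC0-last, the Appendix 2 compartmental results and the primary concentration-QTcF analysis do not depend on this rule.

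Nor do the documents support a conclusion that the reported half-lives are biased: that requires the printed formula to have been used in place of a correct software default. The unstated precedence between visual inspection and the automatic rule needs correcting in either case.

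**What to change.** In the λz row of SAP Appendix 1:

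1. Print Adjusted R² = 1 − (1 − R²) × (n − 1)/(n − 2).
2. State that the automatic rule is the default, and that visual inspection serves only for overrides, each documented with its reason.
3. Confirm that the software setting used for λz matches the corrected formula.

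The cost is one operator, one sentence and one check of a setting. No data collection, sample size or primary analysis changes.

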## APPENDIX 2 – CALCULATION OF PHARMACOKINETIC PARAMETER USING COMPARTMENTAL ANALYSIS

- Actual blood sampling times for the assay of MCI-186 will be used in the calculation of pharmacokinetic parameters.
- All concentrations below the LLOQ will be set at missing for pharmacokinetic calculations.
- In this model, use the three-compartment model as shown in the figure.

- Plasma concentration formula in infusion ( $0 < t < T$ ) is as follows.

$$C_p(t) = \frac{A(1 - e^{-\alpha t})}{\alpha T} + \frac{B(1 - e^{-\beta t})}{\beta T} + \frac{C(1 - e^{-\gamma t})}{\gamma T}$$

- Plasma concentration formula after the end of infusion ( $T \leq t$ ) is as follows.

$$C_p(t) = \frac{A(1 - e^{-\alpha T})}{\alpha T} e^{-\alpha(t-T)} + \frac{B(1 - e^{-\beta T})}{\beta T} e^{-\beta(t-T)} + \frac{C(1 - e^{-\gamma T})}{\gamma T} e^{-\gamma(t-T)}$$

A, B and C are coefficients which describe the exponential functions of each phase

$\alpha$ ,  $\beta$  and  $\gamma$  are exponents which describe the shape of the curve for each phase

WinNonlin PK Parameter Calculation Settings	
Model Selection	Model 19 (Three-compartment, IV-infusion, and first-order elimination rate without lag time model)
Mappings	Subject id, Dose, Time, Concentration
Weighting	1/Yhat
Parameter Options	WinNonlin Generated Initial Parameter Values / WinNonlin Bounds
Minimization	Gauss-Newton (Levenberg and Hartley)
Increment for Partial Derivatives	0.001

WinNonlin PK Parameter Calculation Settings	
Meansquare	---
Iterations	50
Convergence criteria	0.0001

PK Parameter Calculations		
Parameters	Unit	Calculation
A	ng/mL	$A = \frac{D(k_{21} - \alpha)(k_{31} - \alpha)}{V_1(\gamma - \alpha)(\beta - \alpha)}$ 
An initial value is obtained from the above relational formula, and an estimated value is calculated using a nonlinear least squares method.

B	ng/mL	$B = \frac{D(k_{21} - \beta)(k_{31} - \beta)}{V_1(\gamma - \beta)(\alpha - \beta)}$ 
An initial value is obtained from the above relational formula, and an estimated value is calculated using a nonlinear least squares method.

C	ng/mL	$C = \frac{D(k_{21} - \gamma)(k_{31} - \gamma)}{V_1(\alpha - \gamma)(\beta - \gamma)}$ 
An initial value is obtained from the above relational formula, and an estimated value is calculated using a nonlinear least squares method.

$\alpha$	1/h	$\alpha = \frac{k_{21} \cdot k_{31} \cdot k_{el}}{\beta \cdot \gamma}$ 
An initial value is obtained from the above relational formula, and an estimated value is calculated using a nonlinear least squares method.

$\beta$	1/h	$\beta = \frac{k_{21} \cdot k_{31} \cdot k_{el}}{\alpha \cdot \gamma}$ 
An initial value is obtained from the above relational formula, and an estimated value is calculated using a nonlinear least squares method.

$\gamma$	1/h	$\gamma = \frac{k_{21} \cdot k_{31} \cdot k_{el}}{\alpha \cdot \beta}$ 
An initial value is obtained from the above relational formula, and an estimated value is calculated using a nonlinear least squares method.

PK Parameter Calculations		
Parameters	Unit	Calculation
$V_1$	L	$V_1 = \frac{D}{A + B + C}$
$k_{el}$	1/h	$k_{el} = \frac{CL}{V_1}$
$k_{21}$	1/h	$k_{21} = \frac{\alpha \cdot \beta \cdot \gamma}{k_{el} \cdot k_{31}}$
$k_{31}$	1/h	$k_{31} = \frac{\alpha \cdot \beta \cdot \gamma}{k_{el} \cdot k_{21}}$
$C_{max}$	ng/mL	will be determined using maximum drug concentration
$t_{1/2\alpha}$	h	$t_{1/2\alpha} = \frac{\ln(2)}{\alpha}$
$t_{1/2\beta}$	h	$t_{1/2\beta} = \frac{\ln(2)}{\beta}$
$t_{1/2\gamma}$	h	$t_{1/2\gamma} = \frac{\ln(2)}{\gamma}$
$AUC_{0-\infty}$	h·ng/mL	$AUC_{0-\infty} = \frac{A}{\alpha} + \frac{B}{\beta} + \frac{C}{\gamma}$
CL	L/h	$CL = \frac{D}{AUC_{0-\infty}}$
MRT	h	$AUMC = \frac{A}{\alpha} \left( \frac{T}{2} + \frac{1}{\alpha} \right) + \frac{B}{\beta} \left( \frac{T}{2} + \frac{1}{\beta} \right) + \frac{C}{\gamma} \left( \frac{T}{2} + \frac{1}{\gamma} \right)$ $MRT = \frac{AUMC}{AUC_{0-\infty}}$
$V_{ss}$	L	$V_{ss} = CL \cdot MRT$

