APPENDIX 2 – CALCULATION OF PHARMACOKINETIC PARAMETER USING COMPARTMENTAL ANALYSIS.....	29

Abbreviations

AE	:	adverse event
BLQ	:	below limit of quantification
BMI	:	body mass index
CV	:	coefficient of variation
DBL	:	database lock
DP	:	decimal places
ECG	:	electrocardiogram
IAO	:	International agreed order
IMP	:	investigational medicinal product
LLOQ	:	lower limit of quantification
MedDRA:		Medical Dictionary for Regulatory Activities
PK	:	pharmacokinetics
PT	:	preferred term
QC	:	quality control
SAP	:	statistical analysis plan
SAE	:	serious adverse event
SD	:	standard deviation
SOC	:	system organ class
TEAE	:	treatment emergent adverse event
WHO-DD:		World Health Organization Drug Dictionary

List of PK Parameters		
Parameters	Unit	Definitions
$\alpha$	1/h	Elimination rate constant of the $\alpha$ -phase
$AUC_{0-\text{last}}$	h*ng/mL	Area under the concentration-time curve from time zero to the last quantifiable concentration time point
$AUC_{0-24h}$	h*ng/mL	Area under the concentration-time curve from time zero to 24h
$AUC_{0-\infty}$	h*ng/mL	Area under the concentration-time curve from time zero to infinity
$AUC\%_{\text{ex}}$	%	Area under the plasma concentration-time curve extrapolated from the last quantifiable concentration time point to infinity in % of the total $AUC_{0-\infty}$
$\beta$	1/h	Elimination rate constant of the $\beta$ -phase
CL	L/h	Total clearance
$C_{\text{max}}$	ng/mL	Maximum plasma concentration
$\gamma$	1/h	Elimination rate constant of the $\gamma$ -phase
$k_{21}$	1/h	Transfer rate constant from peripheral (2) to central (1) compartment
$k_{31}$	1/h	Transfer rate constant from peripheral (3) to central (1) compartment
$k_{\text{el}}$	1/h	Elimination rate constant from the central compartment in compartmental analysis
Lower limited of $\lambda_z$	h	Lower data point used for the estimation of $\lambda_z$
MRT	h	Mean residence time
Number of $\lambda_z$ points	-	Number of data point used for the estimation of $\lambda_z$
A	ng/mL	Zero-time intercept for $\alpha$ -phase
B	ng/mL	Zero-time intercept for $\beta$ -phase
C	ng/mL	Zero-time intercept for $\gamma$ -phase
$\lambda_z$	1/h	Elimination rate constant in non-compartmental analysis
$t_{1/2}$	h	Terminal elimination half-life in plasma concentration-time course
$t_{1/2\alpha}$	h	Half-life at $\alpha$ -phase
$t_{1/2\beta}$	h	Half-life at $\beta$ -phase
$t_{1/2\gamma}$	h	Half-life at $\gamma$ -phase
$t_{\text{max}}$	h	Time of maximum plasma concentration after administration

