List of PK Parameters		
Upper limited of $\lambda_z$	h	Upper data point used for the estimation of $\lambda_z$
$V_1$	L	Volume of the central compartment
$V_{ss}$	L	Volume of distribution at Steady State
$V_z$	L	Volume of distribution during terminal phase

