### **7.8.2 Analysis of Pharmacokinetic Parameters**

All PK parameters will be listed.

The PK parameters will be summarized by each MCI-186 group (60 mg group and 300 mg group). The following descriptive statistics will be calculated: N (number of subjects), n (number of valid observations), arithmetic mean, SD, CV%, minimum, median, maximum, geometric mean and geometric CV%.

For the descriptive statistics, the minimum and maximum will be presented according to following requirement:

- $C_{\max}$ , A, B, C will be presented with the number of significant digits they are reported with.
- Other PK parameters: will be presented with a fixed number of decimal places for each parameter. The number of decimal places is 2 decimal places corresponding to having 3 significant digits at the minimum by analyte.

Mean, SD, median and geometric mean will be presented with the number of decimals as follows.

- $C_{\max}$ , A, B, C: will be presented with 4 significant digits.
- Other PK parameters: will be presented with 2 decimal places.

CV% and geometric CV% will be presented with 1 decimal place.

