## **11. VALIDATIONS**

SAS® for Windows (release 9.2 or a later version) will be used for statistical analyses.

Phoenix® WinNonlin® (release 6.3 or a later version) will be used to calculate Pharmacokinetics Parameters.

The quality of statistical results will be ensured by double programming at [REDACTED]

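### SAP Appendix 2 leaves the infusion half-time in the compartmental MRT, so Vss = CL × MRT as written exceeds the model's own steady-state volume by CL × T/2 (about 22 L at 60 mg).

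*SAP*

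**What the plan says.** **Compartmental analysis (SAP Appendix 2).** The model is a three-compartment intravenous infusion. One concentration equation applies during the infusion (0 < t < T). The other is introduced as "Plasma concentration formula after the end of infusion" (T ≤ t), so T is the infusion duration. The parameter table then gives:

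- AUC0-∞ = A/α + B/β + C/γ
- CL = D/AUC0-∞
- AUMC = (A/α)(T/2 + 1/α) + (B/β)(T/2 + 1/β) + (C/γ)(T/2 + 1/γ)
- MRT = AUMC/AUC0-∞; in formula source, the end of this row reads "C}{\gamma} \left( \frac{T}{2} + \frac{1}{\gamma} \right)$ $MRT = \frac{AUMC}{AUC_{0"
- Vss = CL × MRT

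**Non-compartmental analysis (SAP Appendix 1).** MRT is formed as "AUMC}_{0-\infty}}{\text{AUC}_{0-\infty}} - \frac{\text{TI}}{2", "where TI represents infusion duration", and Vss is again MRT × CL.

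**Definitions and reporting.** The SAP's List of PK Parameters has a single entry for MRT ("Mean residence time") and a single entry for Vss ("Volume of distribution at Steady State"), serving both appendices. SAP 7.8.2 states "All PK parameters will be listed". SAP 12.1 and 12.2 give the compartmental parameters their own listing and summary table. SAP 11 says that Phoenix WinNonlin "will be used to calculate Pharmacokinetics Parameters".

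**The concern.** The two appendices use the same relation for Vss but feed it different MRTs. For drug given by infusion, AUMC/AUC is the mean time from the start of the infusion. It includes the average time a molecule waits to be infused, which is T/2 at a constant rate. Steady-state volume is clearance multiplied by the time spent in the body after entry, so T/2 has to come out before multiplying by CL. Appendix 1 takes it out and Appendix 2 does not.

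PK parameters are a secondary endpoint (SAP 2.1.4). If the Appendix 2 formulas are applied as written, the compartmental Vss column is not a steady-state volume, and MRT has a different meaning in the two PK tables with nothing to warn the reader. The reach is limited to those two parameters. Cmax, AUC, CL, V1, the half-lives, every non-compartmental parameter and the primary concentration–QTcF model are untouched.

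**Working it through.** The plan states no value of MRT or Vss, so there is no figure to reproduce. The check is algebra, a numerical confirmation, and a size from the plan's simulated exposure.

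**Inputs**

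| Input | Value | Source |
|---|---|---|
| Dose, infusion duration | 60 mg, T = 1 h | SAP 1.1 |
| Simulated single-dose AUC | 1364.7 ng·h/mL | Protocol 3.4.1 |
| Dose behind that AUC | 60 mg, inferred | Protocol 3.4.1 gives Cmax 1047.3 ng/mL; Protocol 1.2.2 gives 1047 ng/mL for 60 mg over 60 min |
| Anticipated Cmax at 60 and 300 mg | 1041 and 6117 ng/mL | Protocol 3.4 |

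**Step 1. Algebra.** Take T/2 out of each AUMC term:

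AUMC = (T/2)(A/α + B/β + C/γ) + (A/α² + B/β² + C/γ²)

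Divide by AUC0-∞ = A/α + B/β + C/γ:

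MRT as written = T/2 + S, where S = (A/α² + B/β² + C/γ²)/(A/α + B/β + C/γ)

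S is the disposition mean residence time, and the model's steady-state volume is CL × S = V1(1 + k12/k21 + k13/k31). Therefore:

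Vss as written − model Vss = CL × T/2 = Dose × T/(2 × AUC)

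The rate constants drop out.

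**Step 2. Numerical confirmation on an assumed profile.** Half-lives 0.389, 0.6 and 5 h; AUC shares 75%, 20% and 5%; T = 1 h; AUC 1364.7; 60 mg.

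- S = (0.75 × 0.389 + 0.20 × 0.6 + 0.05 × 5)/ln 2 = 0.955 h.
- Integrating t × C(t) over Appendix 2's concentration equations gives 1985.23, equal to its closed-form AUMC. AUMC is therefore the moment of the infusion curve.
- MRT as written = 1985.23/1364.7 = 1.455 h; Vss as written = 63.96 L.
- V1(1 + k12/k21 + k13/k31) = 41.97 L. The difference is 21.98 L.

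Three other assumed sets of rate constants, with the same AUC and T, give the same gap:

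| Set | Vss as written (L) | Model Vss (L) | After subtracting T/2 (L) |
|---|---|---|---|
| 1 | 95.32 | 73.33 | 73.33 |
| 2 | 88.65 | 66.67 | 66.67 |
| 3 | 95.98 | 74.00 | 74.00 |

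**Step 3. Size at 60 mg.** CL = 60,000 µg ÷ 1364.7 µg·h/L = 43.97 L/h.

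- T = 1 h: 43.97 × 0.5 = 21.98 L.
- T = 0.95 to 1.05 h (assumed range): 43.97 × 0.475 = 20.9 L to 43.97 × 0.525 = 23.1 L.

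**Step 4. Size at 300 mg.** The documents give no AUC, so one is assumed.

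- AUC in proportion to dose (5-fold): 300,000/(5 × 1364.7) × 0.5 = 21.98 L.
- AUC rising with anticipated Cmax (6117/1041 = 5.876-fold): 300,000/(5.876 × 1364.7) × 0.5 = 18.71 L.

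**Step 5. What the two tables would show.** By definition the MRTs differ by T/2 = 0.5 h. The visible gap will not be exactly that, because Appendix 1 also carries trapezoid and sampling error. On the Step 2 profile, sampled at nominal times plus 5 minutes with no quantification cut-off, the Appendix 1 procedure gives MRT 1.044 h and Vss 47.54 L. The gaps to Appendix 2 are 1.455 − 1.044 = 0.41 h and 63.96 − 47.54 = 16.4 L.

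**The case against.** Four arguments can be made for leaving this alone.

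- **The software does the work.** SAP 11 assigns the calculation to WinNonlin, and parts of the Appendix 2 table cannot be a working recipe: k21 is defined from k31 and k31 from k21. The table may only document relations, and the error may never reach an output. This stands as a limit: no wrong reported value has been shown. It does not rescue the text, because the MRT and Vss rows can be computed exactly as written. If the software removes T/2, the SAP misdescribes what is reported; if it does not, the reported Vss is wrong.
- **An MRT that includes input time is a legitimate quantity.** Agreed. For MRT alone the defect is inconsistency with Appendix 1 under a shared name. The argument does not extend to Vss, since CL × (S + T/2) is not a steady-state volume.
- **The parameters are descriptive.** Also true. No test, decision rule or dose argument uses Vss or MRT, and Appendix 1 reports both with the correction. This bounds the importance, but the compartmental column is still published under the same name.
- **The litre figure rests on an inference and has no denominator.** Protocol 3.4.1 does not state the dose behind its AUC, and the matching 1047 ng/mL in Protocol 1.2.2 is after 14 daily doses. The link is sound, since Protocol 3.4.1 gives nearly identical single-dose and steady-state values (the steady-state AUC of 1373.9 gives 21.84 L), but it remains an inference. The documents give no Vss, so no percentage error is claimed. For scale only, 21.98 L would be 44% of an assumed 50 L and 15% of an assumed 150 L.

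**Conclusion.** The concern holds. The Appendix 2 Vss formula is wrong as written, and its MRT is not the quantity Appendix 1 defines under the same name. The excess in Vss is exactly CL × T/2 for each subject. That is about 22 L at 60 mg, assuming the simulated AUC of 1364.7 ng·h/mL belongs to that dose and T = 1 h. At 300 mg it is about 18.7 to 22.0 L under the assumed range of AUC. The compartmental MRT is T/2 (0.5 h at the planned duration) longer by definition. Whether any reported number is wrong depends on whether the written formula was used, which the documents do not settle. The point is worth correcting, but its reach ends at two descriptive parameters in one listing and one table.

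**What to change.** In SAP Appendix 2, write MRT = AUMC/AUC0-∞ − T/2, with T the infusion duration used in the fit, and keep Vss = CL × MRT. Both appendices then define the same quantities.

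Then check the compartmental outputs. From each subject's A, B, C, α, β and γ (unrounded, since the rate constants enter squared), compute S = (A/α² + B/β² + C/γ²)/(A/α + B/β + C/γ).

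- If the reported MRT equals S, the software already removed T/2 and only the SAP text needs correcting.
- If it equals S + T/2, the written formula was used. Subtract T/2 from MRT and CL × T/2 from Vss for each subject, using the T in that subject's fit, and rerun the summaries. Actual infusion start and end times are recorded (Protocol 7.1.1) if the fit used them.

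The cost is one formula line and a short check on parameters already listed. At worst, two columns in one listing and one table are recomputed. There is no refit and no effect on trial conduct.
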